3 ANALYSIS SETS

An analysis data set will be created for each efficacy and safety assessment. In addition to reported data values, each analysis data set will include derived variables as specified in Section 4 (e.g., baseline, total, and change from baseline values). All analysis data sets will also include key study- and subject-level information (including but not limited to: study identifier, study site identifier, subject identifier, age, sex, race, randomization number, analysis set eligibility flags, randomized treatment, actual treatment received, study treatment start and stop dates, reason for discontinuation [if applicable], and age strata).

Figure 1: Study design (Parts A and B)

All data analyses will be performed using at least one of the following analysis sets. Subject eligibility for each analysis set will be finalized before unblinding of the data, where applicable.

3.1 Intent-to-treat analysis set

The intent-to-treat (ITT) analysis set includes all subjects who are randomized and dispensed study drug at the Baseline Visit (Visit 2). Subjects will be categorized according to randomized treatment. This analysis set will be used for all demographics, baseline characteristics, and prior medication analyses.

3.2 Safety analysis set

The safety analysis set will include all subjects who are randomized and take at least one dose of randomized study drug during this trial. Subjects will be categorized according to actual treatment received. This analysis set will be used for all concomitant medication, study drug exposure, and safety analyses.

3.3 Full analysis set

The full analysis set will include all randomized subjects who took at least one dose of randomized study drug and have a valid baseline ADHD-RS-5 assessment and at least 1 valid post baseline ADHD-RS-5 assessment. Subjects will be categorized according to randomized treatment. This analysis set will be used for all efficacy analyses.

3.4 Per-protocol analysis set

The per-protocol (PP) analysis set is a subset of the full analysis set which will include data from subjects who do not have any significant protocol deviations. Subjects will be categorized according to actual treatment received. This analysis set will be used for sensitivity analyses to examine the robustness of the ITT results for the primary efficacy variable and key secondary efficacy variables.

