CRITERIA FOR EVALUATION	Efficacy in each part of the study will be assessed using the ADHD-RS-5, CGI-I, CGI-S and Conners 3-P(S) scales.  Safety in each part of the study will be assessed by evaluating TEAEs, vital signs measurements (including systolic blood pressure, diastolic blood pressure, pulse rate, respiratory rate, and temperature), measurements of weight, and responses on the C-SSRS.
STATISTICAL METHODS	Study Populations:  The Intent-to-Treat Population of each part of the study includes all subjects who are randomized and dispensed study medication at the Baseline visit. The Full Analysis Set of each part of the study includes all subjects who are randomized, take at least one randomized dose of study medication during this trial, and have a valid Baseline and at least one post-Baseline follow-up assessment of the primary outcome measure - ADHD-RS-5 total score. The Safety Population of each part of the study includes all subjects who are randomized and take at least one randomized dose of study medication and during this trial.
	General Considerations:  Randomization will be implemented in a 1:1 ratio using a computer-generated schedule stratified by age (6 to 12, 13 to 17 years old) and part (A, B). Each part of the study will be analyzed separately. Pooled analyses using both parts may also be conducted, if appropriate. Experimental results will be summarized with descriptive statistics and will be presented by treatment group (AEVI-001 or placebo) and overall. Continuous endpoints will be summarized by the number of subjects (n), mean, median, standard deviation (SD), minimum, and maximum. Categorical and count endpoints will be summarized using n and the percentage of subjects in each category.
	All statistical tests will be 2-sided and performed at the 0.05 level of significance. All confidence intervals (CIs) will be 2-sided 95% CIs. All efficacy analyses will be

conducted using the Full Analysis Set; all safety analyses will be conducted using the Safety Set.

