### 9.7 Dose Adjustment Criteria

The duration of the dose-optimization phase is 4 weeks to allow for weekly titration up to the highest dose and 1 titration down to the previous dose, if necessary.

Following enrollment, all subjects will begin taking AEVI-001 or placebo and will be evaluated after approximately 7 days ( $\pm$  2 days) for safety and efficacy. Subjects may be titrated weekly to the next available dose strength after approximately 7 days ( $\pm$  2 days) on the previous dose, based on the overall response of the subject. Additionally, if needed, a subject may be down-titrated once to the previous dose level to optimize tolerability and efficacy. Subjects unable to tolerate the lowest available dose (100 mg twice daily or placebo) will be discontinued from the study. Subject response will be categorized by the investigator as 1 of 3 conditions and associated actions, with titration continuing until an "acceptable response" is achieved:

□ Intolerable response (i.e., intolerable side effects): Requires the subject to be tapered to a lower dose of AEVI-001 or placebo (if available). However, if this lower dose produces an intolerable response as well, the subject should be discontinued from the study.
 □ Ineffective response: Subject has not achieved a CGI-I score of <3. This response requires increasing titration of AEVI-001 or placebo to the next available dose strength, provided tolerability is acceptable, followed by weekly evaluation.

 □ Acceptable response: A response is defined as acceptable if it shows a significant reduction in symptoms, defined by a CGI-I score of <3, with tolerable side effects. Subjects categorized as "acceptable" may be maintained at their current dose of AEVI-001 or placebo for the remainder of the study. Subjects who are tolerating IP at the highest

available dose but do not achieve an acceptable response should be continued in the study.

If, in the opinion of the investigator, the "acceptable" dose is well tolerated and the subject would potentially receive additional symptom reduction, the dose may be increased to the next dosage strength.

If, in the opinion of the investigator, the subject experiences unacceptable tolerability, the dose of AEVI-001 or placebo may be reduced (if available) by 1 dose level (to the previous dose). If the subject tolerates the dose reduction and maintains symptom control, the subject may be maintained at that reduced dose for the remainder of the study.

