### 14.1 Study Endpoints

### 14.1.1 Efficacy

In each part of the study, the primary outcome will be the change from baseline in the ADHD-RS-5 total score at Visit 8 (Week 6), where baseline is defined as the last ADHD RS-5 total score assessment prior to the first dose of investigational product (usually at Visit 2/Day 0).

The primary efficacy analysis will be conducted using the Full Analysis Set for the change from baseline for the ADHD-RS-5 total score, including all assessments from Visit 3 (Week 1) up to Visit 8 (Week 6), using the linear mixed models repeated measures (MMRM) methods with treatment group, visit, and baseline ADHD-RS-5 total score as a covariate, and interaction of the baseline ADHD-RS-5 total score with the visit included in the model. Missing data will not be imputed.

The primary contrast of interest will be the comparison of the AEVI-001 and placebo groups at Visit 8 (Week 6).

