2.3 Determination of sample size

For Part A of the study, 42 unique subjects are planned to be randomized to yield approximately 34 subjects who provide post-baseline efficacy data on the primary endpoint. Assuming an effect size of 1.0, this number will yield approximately 80% power to detect a significant difference in mean change from baseline for the ADHD-RS-5 total score at Visit 8 (Week 6) between the treatment groups, based on a 2-tailed test with $\alpha = 0.05$ and 1:1 randomization. In Part A of the study, an interim analysis will be performed when approximately 75% of randomized subjects have completed the study. The sample size could be increased to 64 randomized subjects.

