5.3 Primary efficacy analysis

The change from baseline in ADHD-RS-5 total score will be analyzed with mixed model repeated measures (MMRM) methods using the full analysis set. The model will include derived visit (see Section 4.7), age stratum, treatment group, and treatment-by-visit interaction as fixed factors and baseline ADHD-RS-5 total score as a covariate. Robust variance estimates for the fixed effects will be used for testing treatment differences. Within subject variability will be modeled using an unstructured (i.e., TYPE = UN) covariance pattern. In case of convergence problems, a banded Toeplitz (i.e., TYPE = TOEP(5)) structure for the covariance pattern will be used. The comparison of interest will be the difference between the AEVI-001 and placebo treatment groups at Visit 8. Model based point estimates (i.e., least square [LS] means for each treatment group and the treatment difference), 95% confidence interval for the difference, p-value, and effect size will be reported for each derived visit. Effect size will be calculated as the LS mean difference divided by an estimate of the pooled standard deviation.

Similar MMRM methods will be used to test for treatment differences in each CNTN4 CNV subgroup (see Section 4.3.8 for definition of CNTN4 CNV indicator). To control the overall type I error rate for these subgroup comparisons, a hierarchical testing procedure will be used with comparisons of the primary efficacy variable tested in the following fixed sequence:

- Full analysis set
- Full analysis set CNTN4 CNV subgroup
- Full analysis set Non-CNTN4 CNV subgroup

Supportive MMRM analyses of the primary endpoint will also be performed using the PP analysis set.

Descriptive statistics for the ADHD-RS-5 total score and change from baseline in ADHD-RS-5 total score will be presented by treatment group and derived visit. A similar descriptive statistics display will also be presented by CNTN4 CNV indicator and age stratum.

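### The per-protocol MMRM is offered as a check on ITT efficacy results that do not exist, and no planned analysis of the primary endpoint tests the missing-at-random assumption or covers all randomised subjects

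*SAP*

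**What the plan says.** SAP 3.1 defines the ITT set as subjects randomised and given drug at the Baseline Visit, and limits its role: "This analysis set will be used for all demographics, baseline characteristics, and prior medication analyses". SAP 5.2 adds the summary of major deviations. Efficacy does not appear.

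SAP 3.3 gives all efficacy work to the full analysis set, whose members must "have a valid baseline ADHD-RS-5 assessment and at least 1 valid post baseline ADHD-RS-5 assessment". SAP 5.3 fits the primary MMRM to that set, with unstructured covariance and the treatment contrast at Visit 8. Protocol 14.1.1 adds: "Missing data will not be imputed".

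SAP 3.4 defines the per-protocol set as the part of the full analysis set without significant deviations, grouped by treatment actually received. Its stated use is "sensitivity analyses to examine the robustness of the ITT results for the primary efficacy variable". SAP 5.3 carries this out: "Supportive MMRM analyses of the primary endpoint will also be performed using the PP analysis set". The only other models for the primary variable are CNTN4 subgroup MMRMs, again on the full analysis set.

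On expected attrition, SAP 2.3 says: "42 unique subjects are planned to be randomized to yield approximately 34 subjects who provide post-baseline efficacy data on the primary endpoint".

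**The concern.** There are two linked problems. The first is wording: SAP 3.4 names a result that the plan never produces. The second is substance. A likelihood MMRM without imputation relies on missing at random. Given arm, baseline and the scores already seen, a subject's unseen later scores are taken to behave like those of similar subjects who stayed in the same arm. For a child who stops AEVI-001, that describes Week 6 as if treatment had continued. Whether it also describes Week 6 off the drug cannot be learned from the observed data, so the assumption has to be varied deliberately.

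There is reason to do so here. Protocol 9.7 states: "Subjects unable to tolerate the lowest available dose (100 mg twice daily or placebo) will be discontinued from the study". Protocol 8.7 lists lack of efficacy among the reasons for discontinuation. After the early-termination visit, Protocol 10.1.7 schedules only a telephone call about medications and adverse events, so no Week 6 rating is planned for subjects who have stopped.

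At stake is how the Part A result is read. A per-protocol estimate close to the primary one could be reported as showing robustness, although it says nothing about the missing-data assumption.

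**Working it through.** **1. Set inclusion.** Per-protocol subjects are a subset of the full analysis set (SAP 3.4). Full analysis set subjects are randomised subjects with a dose, a valid baseline and a valid post-baseline rating (SAP 3.3). Moving from the primary to the per-protocol analysis can therefore only keep or remove subjects. The model is unchanged, so the missing-data assumption is unchanged too.

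**2. The plan's own figure.** Inputs from SAP 2.3: effect size 1.0, about 34 subjects with data, 1:1 allocation, two-sided 0.05, about 80% power. The protocol synopsis agrees on the test: "All statistical tests will be 2-sided and performed at the 0.05 level of significance". A two-sample t-test with 17 per arm has noncentrality 1.0 × √(17/2) = 2.92 on 32 degrees of freedom, which gives power of 80.7%. The figure reproduces. Implied loss is (42 − 34)/42 = 8/42 = 19.0%, and 34/(1 − 0.19) rounds up to 42.

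**3. Illustration.** Let d be the effect if everyone had continued (1.00, taken as what the MMRM estimates), f the share of active-arm subjects without data, and r the fraction of benefit they keep. Placebo subjects without data are assumed to resemble those with data.

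Effect in all randomised = d × [1 − f(1 − r)]

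Overstatement by the MMRM = 1/[1 − f(1 − r)] − 1

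Neither f by arm nor r is in the documents; both are assumptions. With equal loss by arm, f = 4/21 = 8/42:

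| r | Effect in all randomised | Below 1.00 by | MMRM figure too high by |
|---|---|---|---|
| 0 | 34/42 = 0.81 | 19.0% | 42/34 − 1 = 23.5% |
| 0.5 | 0.905 | 9.5% | 10.5% |
| 1 | 1.00 | 0% | 0% |

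The two percentages in each row have different denominators and should not be interchanged.

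**4. Range.** With r = 0 and f from 5% to 30%, the all-randomised effect runs from 0.95 to 0.70 (overstatement 5.3% to 42.9%). With r = 1 it is 1.00 throughout. The split of the 8 also matters: 2 in the active arm gives 19/21 = 0.905, and 6 gives 15/21 = 0.71.

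**5. Does this matter at this sample size?** As a rough t-test guide, significance at 17 per arm needs an observed difference of 2.037 × √(2/17) = 0.70 SD. At 21 per arm it needs 2.021 × √(2/21) = 0.62 SD. An observed 0.70 to 0.77 SD would pass in the planned analysis but not after scaling by 34/42, since 0.62/0.81 = 0.77. This holds the SD fixed and ignores imputation uncertainty.

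**6. What the 34 means.** SAP 2.3 does not say whether it counts subjects with any post-baseline rating or with a Week 6 rating. On the first reading, the 8 are exclusions from the full analysis set and later dropouts come on top. On the second, the 8 cover both.

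**The case against.** The group left out entirely may be small. Protocol 9.7 requires subjects who stop for intolerance to complete the early-termination assessments, and Protocol 8.7 asks for them whenever possible in other withdrawals. The SAP's efficacy windows (Table 2) begin at day 1, so a first-week termination rating counts as Visit 3 and brings the subject into the full analysis set. Many early stoppers should therefore be analysed. This stands, and it limits the exclusion problem. It does not supply their Week 6 scores.

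Dropout related to outcome does not by itself break missing at random. If stopping depends on recorded weekly scores, the MMRM accounts for it, and poor scores before stopping lower the implied Week 6 value. Protocol 9.7 also keeps in the study those who tolerate the highest dose without adequate response. A reader might infer that the model simply credits dropouts with the full on-drug course; that goes too far.

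A reader might also infer that the plan would reveal nothing about dropout. That is not so. SAP 5.1.1 tabulates discontinuations, reasons and analysis-set counts by arm, and SAP 5.4 models response and remission with LOCF. These are partial checks: the tables estimate no effect, and the LOCF models use dichotomised secondary endpoints on the same full analysis set.

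Finally, it is tempting to say the per-protocol estimate would shift the same way as any bias and falsely confirm it. The documents do not support this. The exclusions in SAP 4.2 have no stated link to benefit or arm. Under SAP 4.6, expected doses run only to the last intended dose date, so stopping early does not itself produce low compliance.

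**Conclusion.** The gap is real and can be read directly from the SAP. The stated robustness check refers to a non-existent ITT efficacy analysis and cannot test the assumption on which the primary estimate rests. No other planned analysis of the primary endpoint does so or covers all randomised subjects.

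The size is not established. The 0.81 figure requires that the 8 expected losses fall equally by arm and that the active-arm losses keep no benefit; it is one point in a range that includes no bias. A reader might take it as a finding that the trial will overstate its effect by about a fifth. The documents give no loss by arm and no outcome after stopping, and other dropout patterns, such as poor responders leaving placebo, could bias the estimate the other way. That uncertainty is the reason to prespecify a test. The point concerns Part A only, because SAP 1 leaves Part B to a separate SAP. It is a worthwhile, inexpensive improvement and does not fault the choice of the MMRM as primary.

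**What to change.** In the Part A SAP, before unblinding:

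- **5.3:** Keep the MMRM as primary. Add one sensitivity analysis of the Week 6 change in ADHD-RS-5 total score in all ITT subjects with a valid baseline rating. Use reference-based (jump-to-placebo) multiple imputation for scores after discontinuation. Impute subjects with no post-baseline rating from the placebo arm, given baseline score and age stratum.
- **3.4:** Refer to the full analysis set results instead of the ITT results, and describe the per-protocol analysis as supportive only.

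Jump-to-placebo is one of several defensible departures from missing at random. It is proposed because it addresses the case where the benefit ends with treatment, and because it gives subjects without any post-baseline rating a defined place in the analysis.

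The cost is SAP text and one further analysis on data already being collected. The downside is that its estimate may be smaller than the primary one, and the report would have to explain the difference.

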4 DEFINITION OF STUDY VARIABLES

4.1 Subject disposition

The subject number, previous subject number from the Aevi study where genetic testing was performed, informed consent date, screening date, randomization number, and randomization date will be recorded in the Interactive Response Technology (IRT) system and transferred to the electronic case report form (eCRF).

In addition, screen failure date, reason for screen failure, study completion status, the date of study completion or ET, date of last dose, reason for discontinuation, follow-up completion status, date of follow-up telephone call, and date of last contact will be recorded in the eCRF. The reason for screen failure will be recorded as "Does not meet inclusion/exclusion criteria"; "Withdrawal of consent"; "Lost to follow up"; or "Other". Study/follow-up completion status will be recorded as "Yes" or "No". The reason for discontinuation will be recorded as "Adverse Event"; "Lack of efficacy"; "Major protocol deviation"; "Withdrawal by subject"; "Lost to follow up"; "Other"; or "Identity not confirmed".

4.2 **Protocol deviations**

The failure to meet any inclusion/exclusion criteria and the specific criteria not met will be recorded in the eCRF. All subject data will be reviewed for the occurrence of protocol deviations; identified protocol deviations will be captured by the contract research organization (CRO) and categorized as follows:

- Informed consent/assent form
- Inclusion/exclusion criteria
- Concomitant medication
- Study assessments/procedures
- · Investigational product
- Compliance
- Overdose, misuse, and abuse
- Medication error
- Visit window
- Identity confirmation
- Other

In addition to the above categories, all deviations will also be classified as "Major" or "Minor". Major deviations include any deviation from the protocol that could potentially affect the scientific soundness of the research plan or the rights, safety, or welfare of human subjects. The following deviations will be considered "Major", but are not considered all-inclusive as others may be added during the study.

- Failure to obtain written informed consent and assent (if required) from the parent or legally authorized representative and subject, respectively.
- Randomization of a subject who did not meet inclusion criteria.
- Randomization of a subject who met exclusion criteria.
- Use of a prohibited medication on \geq 3 consecutive days during the double-blind treatment period (Visit 2 through Visit 8/ET).
- Protocol defined screening/baseline evaluations needed to assess eligibility were not performed or required results were not obtained prior to randomization.

- Failure to confirm the subject's identity prior to randomization.
- Medication error related to IP dispensation (e.g., incorrect dose, incorrect blister card, etc.).
- Overall noncompliance with IP dosing defined as <80% or >120%.
- Subject overdoses, abuses, and/or misuses the study drug.
- Site failure to follow steps/guidelines/procedures established in the safety monitoring plan such that the safety of the subject or other subjects in the study is potentially endangered.

The Sponsor project team will review all protocol deviations and their major/minor classifications prior to database lock. Subjects with confirmed "Major" protocol deviations will be excluded from the PP analysis set (see Section 3.4).

4.3 Demographics and other baseline characteristics

4.3.1 Age

The date of consent and date of birth will be recorded in the IRT system. In addition, age at informed consent in years and age stratum will be derived within the IRT system. Age stratum will be derived at randomization based on the subject's age at informed consent. Table 1 shows the stratum codes and descriptions assigned to subjects in Part A. Prior to analysis, all age-related data recorded or derived in the IRT system will be transferred into the eCRF.

Table 1: Age stratum codes and descriptions for Part A

Stratum code	Stratum description
1	Age at informed consent 6 to 12 years old, Part A
2	Age at informed consent 13 to 17 years old, Part A

4.3.2 Sex

Sex will be recorded in the IRT system and transferred into the eCRF as "Male" or "Female".

